## Specific Objectives

The primary outcome measure of this study is recovery of peripheral nerve function in type 2 diabetic Veterans. Secondary outcome measures of exercise intervention include changes in aerobic capacity, peak torque, pain perception and health care use. Exercise-induced rehabilitation of diabetic veterans with neuropathy is an overdue concept that remains poorly studied and merits a prospective clinical investigation. Edward Hines, Jr. VA hospital will serve as a readily available resource for completing these studies.

The hypothesis of this study will be tested with the following two *Specific Objectives*:

- a. We will determine the effect of aerobic training, isokinetic strength training, or the combination of aerobic plus isokinetic strength training compared with non-exercise intervention on recovery of peripheral nerve function in age-matched type 2 diabetic Veterans with neuropathy.
  - i. Type 2 diabetic Veterans with established staged length-dependent sensorimotor polyneuropathy will be randomized to a 12 week program of exercise (aerobic, isokinetic, or the combination) or control (non-exercise) intervention. Isokinetic strength promoting leg extensions will be performed on a calibrated Biodex System 3 dynamometer. Aerobic exercise will consist of walking. Sustainability of intervention will be evaluated by repeated testing at 24 weeks. All subject groups will participate in identical biweekly diabetes-related Health Promotion Educational seminars designed to normalize participation.
  - ii. The effects of aerobic training, isokinetic strength training, or the combination of aerobic and isokinetic strength training compared with non-exercise intervention on recovery of peripheral nerve function will be statistically determined from baseline and follow-up testing using a battery of qualitative and quantitative assessments that include clinical history, physical and neurological examination, electrodiagnostic primary outcome measures, Quantitative Sensory Testing, completion of Total Neuropathy Score, visual analogue pain scale, quality of life (SF-36V Health Survey), peak torque (Biodex), peak oxygen uptake (incremental symptom-limited treadmill test) and everyday physical activity (Actical accelerometer physical activity counts).

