**Exercise Interventions:** Aerobic exercise will consist of treadmill walking. Isokinetic strength promoting leg extensions will be performed on a calibrated Biodex System 3 dynamometer. The use of Biodex machine is proposed as an experimental means of determining the impact isokinetic strength training has on recovery of peripheral nerve function in diabetic neuropathic veteran. Demonstrating effect with isokinetic strength training, or in combination with aerobic training, will be used as a strong rationale for implementing interventions of this type into clinical rehabilitative practice. **Subjects randomized to the combined aerobic plus isokinetic strength training** will receive isokinetic strength training followed by aerobic treadmill training so that maximal benefits can be gained from the strength program. Patients will be allowed to rest 15-30 minutes between strength and aerobic training with each session ending with a 10 minute cool-down period. Based on prior experience with exercise intervention studies, we anticipate an 80% retention rate within this intervention group. Our sample size for this group includes a 20% attrition rate to compensate for subjects unable or unwilling to complete the 24-week intervention program. Sustainability of interventions will be evaluated by repeated testing at 24 weeks. **All subject groups will participate in identical biweekly diabetes-related Health Promotion Educational seminars designed to normalize participation.**

Subjects randomized to aerobic, isokinetic, or the combination of aerobic plus isokinetic exercise group will be trained in the Physical Performance Laboratory three times weekly. A 10 minute warm-up consisting of stretching

and flexibility exercises will precede all training sessions. Exercised training duration and intensity will progress as listed in the following table:

Strength Training (maximal isokinetic muscle action; velocity of $90^{\circ} \cdot s^{-1}$ )		Aerobic Training (Walking)
Weeks 1-2	3 sets, 10 repetitions, 1 min rest between sets	25 min at 60-70% $VO_2$ peak; 5 min 71-80% $VO_2$ peak
Weeks 3-4	4 sets, 10 repetitions, 1 min rest between sets	25 min at 60-70% $VO_2$ peak; 10 min 71-80% $VO_2$ peak
Weeks 5-6	5 sets, 10 repetitions, 1 min rest between sets	25 min at 60-70% $VO_2$ peak; 15 min 71-80% $VO_2$ peak
Weeks 7-8	6 sets, 10 repetitions, 1 min rest between sets	25 min at 60-70% $VO_2$ peak; 17 min 71-80% $VO_2$ peak; 3 min 81-90% $VO_2$ peak

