
**Electrodiagnostic Primary Outcome Measures:** Electrodiagnostic findings constitute the primary outcome measures of this study and will be used to define the recovery of peripheral nerve function. Limb temperature will be standardized in this study by using a surface temperature probe integrated with the EMG equipment. Consistent with accepted recommendations, correction factors will NOT be used. The limb surface temperature will be continuously displayed to allow for moment-by-moment monitoring and minimization of variations in limb temperature within and between subjects. Surface temperatures in a limb will be maintained at the same temperature during a subject's sequential nerve conduction studies. For this study, the temperature probe will be placed distally on the leg at the dorsal surface of the ankle and distally on the volar surface of the forearm at the wrist crease. Prior to neurophysiologic evaluation, limbs will be warmed (heating lamp) if the surface temperature is less than 32°C in the leg or less than 33°C at the wrist. If needed, continuous moist heat will be applied to the limb to maintain limb temperature using a hydrocollator heating unit with 4 standard size (10x12 inches) moist heat steam packs. We will measure the following: (i) sensory nerve action potential (SNAP) conduction velocity and amplitude in at least one sural and one median and ulnar nerve (ii) compound muscle action potential (CMAP) conduction velocity, distal motor latency, and amplitude in at least one tibial, peroneal, median and ulnar nerve; and (iii) F-waves from at least one tibial and ulnar nerve. CMAP amplitudes will be measured from baseline to the negative peak, and conduction velocities in the forearm or leg will be calculated by dividing the measured distances (millimeters) between proximal and distal stimulation sites by the difference between proximal and distal onset latencies (milliseconds). F-wave latencies will be recorded as minimal and mean values following 20 stimuli. F-wave recordings will also be obtained from the abductor hallucis muscle stimulating the tibial nerve at the ankle using a prefabricated stimulating and recording array (NC-stat). These recordings will include correction for age, temperature, and height and will be analyzed using a centralized database containing approximately 130,000 validated electrodiagnostic studies providing an unparalleled degree of statistical power with the intent to standardize and enhance the sensitivity of these primary outcome measures. SNAP amplitudes will be measured from the start of the initial negative deflection to the negative peak. Sensory nerve conduction velocities will be calculated by dividing the distance between the stimulating and recording electrodes by the onset latencies. Electrodiagnostic measures of autonomic function will not be evaluated. Normative data appropriate for age range of subjects enrolled in this study are available (Appendix C). F-wave norms are based on regression equations that include variables for both age and limb length.

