### **Statistical Analysis Plan**

In response to reviewer's concerns, we addressed statistical concerns with this program by recruiting the services of [name]. (Associate Professor of Preventative Medicine and Epidemiology and biostatistician, Loyola University Chicago). [name] has generously agreed to serve as lead statistician of this study. He will be responsible for the statistical analyses of all collected study data. The statistical analytical sections of this revised application, including determination of subject sample size, have been substantially revised per the advice of [name].

All data will be entered in SPSS 15 for Windows (SPSS, Inc., Chicago, IL). Results will be expressed as mean  $\pm$  SEM of (n) observations. To directly test the hypothesis that a combined influence of aerobic and isokinetic strength training will enhance recovery of peripheral nerve function, measures of conduction velocity and amplitude will be analyzed by way of a 2 x 2 factorial analysis of covariance followed by a Bonferroni's multiple comparison post-hoc analysis according to the following scheme:

		Isokinetic Strength Training	
		No	Yes
Aerobic Training	No	Sedentary controls	Isokinetic strength exercise
	Yes	Aerobic exercise	Aerobic plus isokinetic strength exercise

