Data collected at 12 weeks will be analyzed, using baseline measurements as a covariate. This will be repeated with the data that are collected at 24 weeks. In both analyses, primary interest will be in the combined aerobic training plus isokinetic strength training interaction. We hypothesize that patients with the combined exercise program will experience the best outcome. Although data will be collected across three time periods (baseline, 12 weeks, and 24 weeks), we have chosen to not employ a repeated measures design. There are two reasons for this: (i) the proposed study is designed to determine the combined influence of aerobic and isokinetic training on recovery of peripheral nerve function, which we believe is best achieved with a factorial design and (ii) our previous experience identified baseline differences among groups of diabetic neuropathy subjects. These group differences will go uncontrolled using a repeated measures design, but can be controlled statistically with analysis of covariance. Therefore, the aerobic plus isokinetic strength training interaction for our primary electrodiagnostic measures will be observed at 12 weeks, controlling for baseline values. This will be done again for the data collected at 24 weeks. A 2 x 2 factorial analysis of covariance also will be conducted with secondary outcome measures such as changes in aerobic capacity, peak torque, pain perception and health care use. Again, data collected both at 12 and 24 weeks will be analyzed using baseline measurements as a covariate. These analyses will allow us to observe the extent to which the secondary measures dovetail with the primary electrodiagnostic measures. In addition, primary outcomes will be correlated with secondary outcomes in order to assess the association of recovery of peripheral nerve function and quality of life. Partial correlation coefficients will be computed at 12 weeks, controlling for baseline values. This will be repeated for the data collected at 24 weeks.

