**Sample Size Estimate:** The requisite sample size for the proposed study has been based upon the primary outcome measure endpoints of conduction velocity and amplitude. In our preliminary studies (see Table 2), we present data from peroneal nerve conduction velocity and amplitude for sedentary and aerobic (PoleStriding) exercise study groups. We use this information for the proposed study. However, we have not conducted strength training studies and, as such, have had to estimate values that we believe are realistic outcomes. The table below is an estimate of the conduction velocity findings for the proposed study.

		Isokinetic Strength Training	
		No	Yes
Aerobic Training	No	38 m/s	39 m/s
	Yes	39 m/s	43 m/s

Using these estimates we have computed that the effect size for the aerobic plus isokinetic strength training interaction is 0.36. From this, computations indicate that 17 subjects per group will provide 80% power with analysis of covariance to detect an effect size of that magnitude using a 0.05 alpha level. In terms of conduction amplitude, the following table is an estimate of the findings for the proposed study. Again, data from our preliminary studies are incorporated.

		Isokinetic Strength Training	
		No	Yes
Aerobic Training	No	1.9 mV	1.9 mV
	Yes	2.4 mV	4 mV

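### The electrodiagnostic primary outcome has no named nerve, visit or success rule, and no error control across nerves, velocity and amplitude, or the 12- and 24-week tests

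*Combined protocol and SAP*

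**What the plan says.** - **Definition of the primary outcome**: the section Electrodiagnostic Primary Outcome Measures in the protocol states that "Electrodiagnostic findings constitute the primary outcome measures of this study and will be used to define the recovery of peripheral nerve function". The section then lists sensory studies in three nerves (sural, median, ulnar), motor studies in four (tibial, peroneal, median, ulnar) and F-waves in two. It ranks none of them.
- **Analysis** (Statistical Analysis Plan): "measures of conduction velocity and amplitude will be analyzed by way of a 2 x 2 factorial analysis of covariance". No nerve is named. The analysis is followed by a Bonferroni "multiple comparison post-hoc analysis according to the following scheme", and the scheme is the 2 x 2 table of the four groups.
- **Visits** (Statistical Analysis Plan): the model is fitted to the 12-week data with baseline as covariate, then repeated for 24 weeks. "In both analyses, primary interest will be in the combined aerobic training plus isokinetic strength training interaction".
- **Role of 24 weeks elsewhere**: "Sustainability of intervention will be evaluated by repeated testing at 24 weeks" (Specific Objectives), and nearly the same sentence under Exercise Interventions: "Sustainability of interventions will be evaluated by repeated testing at 24 weeks". The accelerometry paragraph also labels the 24-week recording a sustainability measure.
- **Sizing** (Sample Size Estimate): the sample size "has been based upon the primary outcome measure endpoints of conduction velocity and amplitude". The planning data are peroneal: "we present data from peroneal nerve conduction velocity and amplitude for sedentary and aerobic (PoleStriding) exercise study groups". Each endpoint is sized at the full 0.05, which is the only place a significance level appears.

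**The concern.** The plan fixes the contrast, which is the interaction. It leaves open the nerve, whether velocity or amplitude (or both) decides, which visit decides, and how many significant results count as recovery. As written it produces several primary tests with no order and no shared error budget. Nothing in it prevents the nerve, parameter, visit and rule from being settled after the code is broken and the results are visible.

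A positive finding in one nerve at one visit could then be reported as recovery of nerve function, and a reader could not tell how many chances there had been to find it. The Specific Objectives present the study as the evidence for bringing exercise therapy into care, so the claim would carry weight.

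**Working it through.** **1. Number of candidate tests** (one nerve of each type; the protocol's minimum, so more are possible)

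- Full battery: sensory 3 x 2 = 6; motor 4 x 3 = 12 (velocity, distal latency, amplitude); subtotal 18. F-waves in two nerves add 2 if counted once (20), 4 as minimal and mean latency (22), or 6 with the separate prefabricated-array recordings (24).
- Velocity and amplitude only, as in the SAP: 3 x 2 + 4 x 2 = 14 per visit, 28 over two visits.
- Narrowest reading, one nerve: 2 per visit, 4 over two visits.

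**2. The plan's own sizing figure**

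For a 1-df interaction in a 2 x 2 ANCOVA with n per group, power comes from the noncentral F distribution with 1 and 4n - 5 df and noncentrality f² x 4n. The stated effect sizes are taken as f on the ANCOVA residual scale.

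- Velocity, f = 0.36, n = 17: noncentrality 0.1296 x 68 = 8.81, df 63, power 83%. At n = 16 it is 81%. The stated 17 per group for 80% is reproduced to within one subject per group.
- Amplitude, f = 0.25: 80% power needs 32 per group. At n = 20 the noncentrality is 0.0625 x 80 = 5.0 and power is 60%. At n = 25 it is 70%.

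**3. Chance of at least one false-positive interaction, if each test is at 0.05 and any one counts**

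Independent tests: 1 - 0.95^k. For correlated tests the documents give no correlations, so I assumed 0.3 to 0.8 between measures and 0.5 to 0.8 between visits. The two-test case is exact bivariate normal; the others are multivariate normal simulation with |z| > 1.96.

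| Reading | k | Independent | Correlated |
|---|---|---|---|
| One nerve, velocity and amplitude, 12 weeks | 2 | 9.8% | 7.8-9.5% |
| Same, both visits | 4 | 18.5% | 12-17% |
| All velocities and amplitudes, 12 weeks | 14 | 51% | 20-44% |
| Same, both visits | 28 | 76% | 29-66% |

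**4. The opposite rule**

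If velocity and amplitude of one nerve at one visit must both be significant at 0.05, and neither has an effect, the error is 0.05² = 0.25% when independent. It is 0.5% at correlation 0.3, 0.9% at 0.5 and 2.2% at 0.8.

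**5. Power under a two-endpoint Holm procedure**

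Same noncentral F as in step 2. The first step is at 0.05/2 = 0.025. The two-step and both-significant figures come from simulation with correlation 0 to 0.8 between the two tests.

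| n per group | Endpoint | At 0.05 | Holm, first step | Holm, both steps | Both significant at 0.05 |
|---|---|---|---|---|---|
| 20 | velocity | 89% | 82% | 83-85% | 53-59% (joint) |
| 20 | amplitude | 60% | 48% | 58-59% | as above |
| 25 | velocity | 95% | 91% | 91-93% | 66-69% (joint) |
| 25 | amplitude | 70% | 59% | 69% | as above |

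The 25-per-group rows apply to the intention-to-treat analysis of all randomized subjects, and only if carried-forward values do not dilute the effect.

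**The case against.** The strongest reply is that the plan is narrower than its list of measures suggests. The SAP confines analysis and sizing to velocity and amplitude, takes its planning data from the peroneal nerve, and names the interaction as the contrast of interest. The sentence about both analyses can be read as ranking the interaction above the main effects, not as making the two visits co-primary. With 24 weeks described elsewhere as sustainability, a fair reader might take 12 weeks as the test of effect. On that reading the 4- and 28-test cases largely fall away. No passage says that one significant result among many would suffice, and independence between nerve measures in the same patient is unrealistic, so 51% and 76% are ceilings.

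Much of this is right as a matter of emphasis. The two- and four-test figures are the ones closest to the SAP, and the any-one rule is an assumption. It does not close the gap. The peroneal nerve is a source of planning values and is never declared the endpoint. The SAP repeats the interaction test for the primary measures at 24 weeks without ranking the visits. Even the narrowest reading leaves two tests at 0.05 with no rule for combining them, and the Bonferroni step does not reach across them. The Preliminary Studies table that the sizing cites is not in the text available, so the statement that no nerve is named primary covers the available text only.

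**Conclusion.** The concern holds. The plan names a primary contrast but no primary nerve, visit or success rule, and it controls error only among the four groups within one model. The family-wise error rate cannot be stated. It ranges from 0.25% under a strict both-significant rule to 76% if any of 28 independent tests counts. On the readings nearest the SAP with an any-one rule, it is 7.8-9.8% (one visit) or 12-18.5% (two visits), above 5% in every case.

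These figures rest on 0.05 per test, on the assumed correlations, and on one nerve of each type. They measure how much the plan leaves undecided; they do not show that error will be inflated. This is an inexpensive improvement, not a flaw in the design. The amplitude endpoint is short of 80% power at 20 per group before any adjustment, which is a separate matter that this change neither causes nor cures.

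**What to change.** Before the code is broken, reconcile the Electrodiagnostic Primary Outcome Measures section with the Statistical Analysis Plan. State the primary nerve or nerves, the parameter or parameters, the visit and the success rule.

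One scheme that fits the sizing:

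- **Primary:** the interaction for peroneal motor conduction velocity and peroneal CMAP amplitude at 12 weeks, tested with Holm at an overall two-sided 0.05.
- **Secondary:** all other nerves and parameters, F-waves and every 24-week test, reported as estimates with 95% confidence intervals and no confirmatory claim.

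The peroneal nerve is only an example, chosen because the sizing data come from it. A single primary endpoint, or a rule that both must be significant at 0.05, would also settle the point. The Exercise Interventions section describes a 12-week training table but also refers once to a 24-week intervention program; those passages should be reconciled when the primary visit is fixed.

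The cost is SAP wording, with no extra subjects or tests. Holm lowers first-step power by about 7 points for velocity and 12 for amplitude at 20 per group. Over both steps most of the amplitude loss is recovered, and velocity stays above 80%. The both-significant rule costs more, with joint power of 53-59% at 20 per group.

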**Whereas electrodiagnostic findings constitute the primary outcome measure of this study (see below), secondary outcome measures of exercise intervention include** changes in aerobic capacity, peak torque, quality of life measures including pain perception and health care use (medications (type and dosage), number of diabetes-related clinical visits, number of diabetes-related hospital admissions and length of stay, number of diabetes-related ER visits). Changes in primary outcome findings will be statistically compared (correlations) with the various secondary measures to determine effect of exercise intervention on quality of life. Our previous experience suggests that improved peripheral nerve function significantly enhances quality of life measures in diabetic subjects. Identifying a correlative statistical relationship between primary and secondary outcome measures, as proposed, will be used as a strong rationale for supporting exercise intervention in the management of diabetic neuropathy in affected Veterans. The clinical history and secondary neurologic findings will be quantitated using previously established and validated measures. Relative neurologic deficits will be quantitated using the Total Neuropathy Score, TNS and NSS. Disability will be graded on a scale of 0 to 5 using a modified Rankin Scale. The specifics of the scoring are shown in Appendix A & B. Health related quality of life will be measured using a SF-36V Health Survey. Pain perception will be evaluated using a validated analogue visual pain scale. Level of chronic physical activity will be quantitated using activity counts from Actical accelerometers. Biceps, triceps, brachioradialis, patellar and Achilles' phasic myotatic ("deep tendon") reflexes will be tested bilaterally in every patient. Diminished reflexes will only be considered abnormal if asymmetric or if different from a previous examination. The subject will be scored 1 point for each diminished reflex and 2 points for an absent reflex for a maximum possible score of 20. This scoring is similar for both the TNS and NSS scores. Vibration, proprioception, pinprick and light touch will be evaluated in every subject. For the NSS, each modality will be given a numerical score of 0 to 5 depending on the degree of sensory deficit. The scores will be added so that a patient could have a maximum score of 20. This is similar to the Sensory Function Score in the TNS. The TNS scale is, however, skewed somewhat distally but also records changes in temperature sensation. Sensory perception will also be assessed by the ability to feel 1 and 10-gram filaments applied to the left large toe and index finger (Sensory Testing Systems, Dallas).

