
**Quantitative Sensory Testing (QST):** QST (Computer Assisted Sensory Evaluator [CASE IV System], WR Medical Electronics, Stillwater MN) is a sensitive quantifiable method for evaluating sensory nerve function. These data will supplement information obtained from clinical and electrodiagnostic examination. We will quantitate vibration (large fiber) as well as cold and heat-pain (small fiber) thresholds. The same technician will conduct all QST studies. The technician will be blinded to the subjects' exercise and clinical/electrodiagnostic status and subjects will be instructed not to discuss their group assignment with the technician. A 4-2-1 methodology will be used. Alternatively, a forced choice paradigm will be employed. Abnormal findings will be defined as outside the 95th percentile of normal limits for gender and age. **Total Neuropathy Score, TNS:** The total neuropathy score is a validated measure of peripheral nerve function and is used as an end point for clinical trials of peripheral neuropathy. The TNS combines information obtained from grading of symptoms, signs, nerve conduction studies, and quantitative sensory tests, and provides a single measure to quantify neuropathy. Inter- and intrarater reliability of the TNS is 0.966 and 0.986, respectively. A cross-sectional validation study showed excellent correlations among all measures of neuropathy. **Modified Rankin Scale:** The modified Rankin scale is a validated measure of disability used as a primary endpoint in clinical trials of acute stroke. The scale describes six grades (0-5) of disability (grade 5, severe disability and bedridden; grade 0, no symptoms). Inter-rater reliability meets criteria for satisfactory clinical assessment (weighted kappa (with quadratic disagreement weights) is 0.91). **SF-36V Health Survey:** Modified from the SF-36, this survey is tailored and validated for the veteran population. The SF-36V is comprised of 8 subscales, all of which have demonstrated high levels of internal consistency and discriminate validity when administered to groups of medically stable individuals. The eight subscales are: physical function, general health, role physical, role emotional, mental health, body pain, vitality and social functioning. The survey will enable monitoring of the subjects' sense of their own well-being, critical for determining whether exercise in Veterans with diabetic neuropathy can produce a meaningful

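### The Total Neuropathy Score contains nerve conduction results, and nothing in the plan keeps it out of the correlations with the electrodiagnostic primary outcome

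*Combined protocol and SAP*

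**What the plan says.** In the methods paragraph headed Electrodiagnostic Primary Outcome Measures, the endpoint is set as follows: "Electrodiagnostic findings constitute the primary outcome measures of this study and will be used to define the recovery of peripheral nerve function". The Statistical Analysis Plan narrows this to the variables analysed: "measures of conduction velocity and amplitude will be analyzed by way of a 2 x 2 factorial analysis of covariance".

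The TNS description, next to Quantitative Sensory Testing (QST), says: "The TNS combines information obtained from grading of symptoms, signs, nerve conduction studies, and quantitative sensory tests". No separate conduction testing for the score is described, so its conduction items presumably come from the same electrodiagnostic sessions as the primary.

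Specific Objective A, part ii, lists the TNS in the battery from which intervention effects are to be determined. The secondary-outcome paragraph of that part plans the correlations: "Changes in primary outcome findings will be statistically compared (correlations) with the various secondary measures to determine effect of exercise intervention on quality of life". It adds that a relationship found this way will be cited in favour of exercise treatment. The same paragraph then turns to the neurologic scales: "The clinical history and secondary neurologic findings will be quantitated using previously established and validated measures", and the TNS is the first scale named.

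The Statistical Analysis Plan repeats the intention: "primary outcomes will be correlated with secondary outcomes in order to assess the association of recovery of peripheral nerve function and quality of life". It uses partial correlations that control for baseline, at 12 and at 24 weeks. After the covariance analyses of the secondary outcomes it says: "These analyses will allow us to observe the extent to which the secondary measures dovetail with the primary electrodiagnostic measures".

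**The concern.** If the primary variable also enters the TNS, it stands on both sides of any TNS-primary correlation. A change in conduction then moves the TNS even when no symptom, sign or sensory threshold has changed. The resulting coefficient mixes two things: a real link between nerve conduction and the other features of neuropathy, and the arithmetic of a part correlated with its own whole.

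This matters because the protocol intends to use primary-secondary correlations as an argument for exercise. A significant TNS coefficient, or a full-TNS treatment effect that runs parallel to the primary, could be taken for corroboration when part of it is the same data counted twice. The primary analysis of covariance is not touched.

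**Working it through.** The plan gives no figure for a TNS-primary correlation, so there is nothing to reproduce. The check asks how large the built-in part could be.

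**Inputs from the documents**
- Score composition: four sources, one of them nerve conduction (TNS description).
- Subjects: 20 per group for analysis, 4 × 20 = 80; 100 randomized (Sample Size Estimate).
- Alpha: 0.05, stated for the sample size. None is stated for the correlations.

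**Assumptions**
- Two-sided test, with two control variables (the baseline of each measure).
- *s*: the share of TNS variance due to conduction items. The scoring appendix is not in the supplied text, so *s* is varied.
- ρ: the correlation of the analysed primary variable with those items. The text does not say which conduction parameters enter the score, so ρ is varied.
- The other TNS items are unrelated to conduction. This isolates the built-in part.

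**Step 1. Significance limit**

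r = t / √(df + t²), with df = N − 2 − 2.
- N = 80: df = 76, t = 1.992, r = 1.992 / √(76 + 3.967) = 0.223.
- N = 100: df = 96, r = 0.199.

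**Step 2. Built-in correlation**

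Write TNS = C + R, where C is the conduction part and R is unrelated to both C and the primary. Then |r| = ρ × SD(C)/SD(TNS) = ρ√s. The chance of p < 0.05 uses Fisher's z with standard error 1/√(80 − 2 − 3) = 0.115.

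| s | ρ | \|r\| = ρ√s | Chance of p < 0.05, N = 80 |
|---|---|---|---|
| 10% | 1 | 0.32 | 81% |
| 20% | 1 | 0.45 | 99% |
| 25% | 1 | 0.50 | 99.7% |
| 40% | 1 | 0.63 | about 100% |
| 25% | 0.6 | 0.30 | 76% |
| 25% | 0.3 | 0.15 | 26% |
| 25% | 0 | 0 | 5% |

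Absolute values are shown. The sign would be negative if a higher TNS means worse neuropathy (an assumption).

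**Step 3. Check with graded items and baseline control**

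A simulation used 2,000 runs with N = 80. It took k equally weighted independent items in five grades, one of them a grading of the primary variable. The baseline-to-follow-up correlation was set at 0.7 (assumed), and both baselines were controlled.

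| k | Mean \|r\| | Significant runs |
|---|---|---|
| 4 | 0.44 | 99% |
| 5 | 0.40 | 96% |
| 7 | 0.33 | 87% |
| 10 | 0.28 | 70% |

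Grading lowers the coefficient somewhat (0.44 against 0.50 for one item in four) but does not remove it.

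**Step 4. Effect of removing the conduction items**

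Under the Step 2 assumptions, r returns to 0 and the false-positive rate to 5%. A real association survives removal. Take four equal-variance sources with pairwise correlation 0.2 and let the primary be the conduction source:
- With the full score: (1 + 3 × 0.2)/√(4 + 12 × 0.2) = 1.6/√6.4 = 0.63.
- With the three remaining sources: (3 × 0.2)/√(3 + 6 × 0.2) = 0.6/√4.2 = 0.29.

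The second figure is the one that carries information about the rest of the neuropathy.

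**The case against.** The strongest reply is that no sentence plans a TNS-primary correlation. The TNS is absent from the named secondary outcomes in both the methods and the Statistical Analysis Plan. The stated purpose of the correlations is quality of life, which the TNS does not measure. The sentence on how secondary measures dovetail with the primary follows covariance analyses of other named measures. The protocol discloses what the score contains, calls it a measure of peripheral nerve function, and leaves patients' own perception of their health to the SF-36V.

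Most of this stands. A reader might infer that the plan specifies this correlation, or that it offers the TNS as independent clinical confirmation. The documents support neither inference. What remains is a gap. The lists are introduced as examples, and the TNS is described among the secondary neurologic findings in the same paragraph as the correlations. The quality-of-life purpose does not settle the matter either, because the named secondary measures also include aerobic capacity and peak torque.

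A second reply is that the size is unknown. That is correct: 0.50 is one favourable case, and at a 25% share with ρ = 0.3 the built-in coefficient is below the significance limit.

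A third is that the overlap gives no reason to remove QST items. That also stands, because QST supplements the primary and is not part of it.

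**Conclusion.** The concern holds in a limited form and is minor. The overlap between the TNS and the primary is in the protocol's own text, and the plan as written permits, without requiring, a correlation that is partly built in.

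Across the assumptions examined, the built-in coefficient runs from 0 to about 0.63. With the primary identical to the TNS conduction items, it exceeds the limit of 0.22 at N = 80 even at a 10% share. With a looser match it may not. These figures rest on assumed shares and correlations and on the other items being unrelated to conduction; the documents fix none of these.

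It would go too far to conclude that the primary-secondary correlations are invalid as a group. SF-36V, pain, aerobic capacity, peak torque and health care use contain no conduction data.

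**What to change.** Add a short rule to the Statistical Analysis Plan:
- State whether the TNS is a secondary outcome.
- For any correlation or agreement reading against the electrodiagnostic primary, use a TNS computed without its nerve conduction items, or leave the TNS out. QST items may stay.
- Report the full TNS as a measure of overall neuropathy, with the conduction-free version beside it.
- Do not present a full-TNS effect as independent confirmation of the primary.

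The cost is one derived variable and a few sentences. No new data or visits are needed, provided item-level scores are kept. The downside is that the reduced score has less published reliability support; the rater reliabilities that the protocol quotes (0.966 and 0.986) are given for the TNS as a whole. If that is unwelcome, leaving the TNS out of these comparisons loses little. The NSS, as the protocol describes it, scores reflexes and sensory modalities, and it is already collected along with the modified Rankin scale, the pain scale and the SF-36V.
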